15.2.2. Adverse Event reporting processes

Initial SAE reports will be reported to EAE Group if they meet the following minimal criteria:

- a. An identifiable patient
- b. A suspect medicinal product (at least one)
- c. An identifiable reporting source
- d. An event or outcome that can be identified as serious and unexpected Causality assessment will be reported asap.

All serious adverse events must be reported in an expedited manner to DNDi through [contact], whether or not the event is considered medication-related (within **24 hours of awareness of SAE** by the investigator), using the SAE (EAE) report form. This includes a description of the event, onset date and type, duration, severity, relationship to each study drug, outcome, actions taken, and all other relevant clinical and laboratory data.

Event	Time Frame	How to report	Report to
AE	NA (same time frame	AE CRF	Data Management
	as other CRF forms)		Center
SAE	24 hours	AE CRF + EAE (at least	DNDi EAE Group; Data
		email notification shortly	Management Center
		followed by EAE form)	_
Pregnancy*	72 hours	Pregnancy surveillance	DNDi EAE Group; Data
		form	Management Center
Spontaneous Abortion	24 hours	EAE (EAE form) +	DNDi EAE Group; Data
-		Pregnancy surveillance	Management Center
		form	-
Other Pregnancy Outcome	72 hours	Pregnancy surveillance	DNDi EAE Group; Data
incl. birth		form and Child	Management Center
		surveillance form	-

*if pregnancy leads in a reportable SAE, EAE form is to also be used and reported within 24 hours

The initial SAE report is to be followed by submission of additional information (follow-up SAE form and any other relevant source documents) as they become available.

Any follow-up report should be submitted as soon as possible, preferably within 5 working days.

Timelines for regulatory reporting in Malaysia (NPRA) and Thailand (Thai FDA):

Fatal and life-threatening Suspected Unexpected Serious Adverse Reaction (**SUSAR**) will be notified to National Pharmaceutical Regulatory Agency (NPRA)/Thailand FDA as soon as possible but **no later than** 7 calendar days after first knowledge by the sponsor that a case qualifies, followed by a report as complete as possible within 8 additional calendar days. The report will include an assessment of the importance and implications of the findings, including relevant previous experience with the same or similar medicinal product. Follow-up information will be actively sought and follow-up reports will be submitted to the NPRA/TFDA when it becomes available.

SUSARs that are not fatal or life-threatening will be notified to the NPRA/TFDA/site ECs as soon as possible but **not later than 15 calendar days after first knowledge by the sponsor** that the case meets the minimum criteria for expedited reporting. Follow-up information will be actively sought and follow-up reports will be submitted to the NPRA/TFDA when it becomes available.

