9.3. Concomitant and or prohibited medication/treatment

Investigators must refer to the most updated list in www.hep_druginteractions.org for information on drug-drug interaction as well as the manual of investigator and study drugs investigator's brochure for contraindicated/excluded co-medications.

Sofosbuvir in combination with another direct acting antiviral (DAA) when co-administered with Amiodarone (a medicine used to treat certain heart problems), particularly in patients also receiving beta blockers, or those with underlying cardiac comorbidities and/or advanced liver disease may cause serious symptomatic bradycardia such as near-fainting or fainting, dizziness or light-headedness, malaise, weakness, excessive tiredness, shortness of breath, chest pain, confusion or memory problems^[64]. Subjects on amiodarone are excluded from this study.

Patients treated with medications associated with QT prolongation concurrently or within the 30 days prior to Screening Visit, including: macrolides, antiarrhythmic agents, azoles,

fluoroquinolones, and tricyclic anti-depressants are excluded from the study. Commonly used and essential medications for this study population like methadone and/or efavirenz is allowed as long as the QTcF value at baseline is < 450 milliseconds. A QTcF value increase up to 500 milliseconds during study conduct is accepted.

HIV/HCV co-infected patients not yet on stable antiretroviral therapy or for whom ART treatment initiation maybe scheduled during the study period are excluded from the study.

The following treatments are prohibited and should be discontinued at least one week prior to Day 1 of study drugs administration:

- Strong inhibitors of CYP3A4 are prohibited, including, but not limited to: ketoconazole, troleandomycin, itraconazole, voriconazole, mibefradil, clarithromycin, telithromycin, grapefruit juice and grapefruit-containing products, Seville oranges, juices and products that contain Seville oranges, conivaptan, nefazodone, etc;
- Strong CYP3A4 inducers are prohibited, including but not limited to: rifampin, rifabutin, rifapentin, dexamethasone, phenytoin, carbamazepine, phenobarbital, St John's wort, etc;
- CYP3A substrates with narrow therapeutic index are prohibited, including but not limited to alfentanil, cisapride, dihydroergotamine, ergotamine, fentanyl, pimozide, and quinidine;

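### Section 15.2.2 makes initial SAE reports to the EAE Group conditional on the event being unexpected, while the same section requires every SAE to reach that group within 24 hours

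*Protocol*

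**What the plan says.** Protocol section 15.2.2 contains two rules for when a site reports an SAE to the sponsor.

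- **Conditional rule, at the start of the section:** "Initial SAE reports will be reported to EAE Group if they meet the following minimal criteria". Four items follow: (a) an identifiable patient; (b) "A suspect medicinal product (at least one"); (c) an identifiable reporter; and (d) "An event or outcome that can be identified as serious and unexpected". A line after the list says that causality will follow as soon as possible.
- **Unconditional rule, in the next paragraph:** "All serious adverse events must be reported in an expedited manner to DNDi", "whether or not the event is considered medication-related", with a limit of "24 hours of awareness of SAE" by the investigator. The table below it gives SAEs a 24-hour limit and names the recipient as "DNDi EAE Group; Data" Management Center. It sets no expectedness condition.

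Section 15.2.1 agrees with the second rule. The investigator classes each event as serious or non-serious, and that classification decides the reporting route. SAEs go to the sponsor and the ethics committee without a further filter. Apart from criterion (d), expectedness enters these rules only in the SUSAR paragraphs at the end of section 15.2.2, where the sponsor reports to the Malaysian and Thai regulators.

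**The concern.** Expectedness is normally a sponsor judgement made after a report arrives, to decide whether it must go on to regulators. Here it stands as an entry condition for the site's own report. A site that takes the opening list at its word could conclude that an SAE it regards as expected need not go to the EAE Group, or can wait.

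What is at stake is the completeness and timeliness of serious safety data reaching the sponsor, and through it the DSMB. A rise in the frequency or severity of an already recognised reaction shows up only if expected SAEs are reported too. Section 21.2 also requires the Thai safety reports to list all suspected serious adverse drug reactions, not only the unexpected ones.

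**Working it through.** There is no figure to reproduce, so the check is a comparison of text.

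**Step 1: do the two rules cover the same thing?** Yes. Both concern the report of an SAE from site to sponsor, and the EAE Group is the recipient in the opening sentence and in the table. They are not separate steps that could each have their own criteria.

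**Step 2: apply each rule to the possible cases.**

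| SAE | Opening list, read as a condition | Next paragraph and table |
|---|---|---|
| Unexpected, drug suspected | Report | Report within 24 hours |
| Expected, drug suspected | Fails (d) | Report within 24 hours |
| Unexpected, judged unrelated | Depends on how (b) is read | Report within 24 hours |
| After consent, before any dose | Depends on how (b) is read | Report within 24 hours |

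The second row is a direct contradiction. The third and fourth rows are ambiguous only.

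**Step 3: can (d) be read so that the conflict disappears?** Items (a) and (c) are plainly the minimum content of a valid report, and (b) can be read in the same way. Item (d) cannot. Whether an event is unexpected is a judgement about the event, not a piece of information to be entered, and the list is introduced as a condition.

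**Step 4: could a site apply (d)?** Section 15.2.1 lists what to record for every AE: dates, severity, seriousness, relationship to each product, action taken, treatment, cause and outcome. Section 15.2.2 lists the contents of the SAE report. Neither list includes expectedness, and neither section says how a site should judge it.

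**Step 5: which rule does the rest of the protocol support?** The unfiltered one. Section 15.2.1 lets seriousness alone decide the route. The opening of section 15 counts SAEs from signature of consent, and section 6.3 requires AE or SAE forms for screening failures, who receive no study drug. Reporting therefore does not depend on exposure, and any rewording of (b) must allow for that.

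**The case against.** The strongest reply is that the operative rule is not in doubt. It is phrased as an obligation, its time limit is emphasised, it follows the list immediately, and it is repeated in the table and in section 15.2.1. A site would have to follow one adjective against several unconditional statements. This stands, and it limits the size of the point: withholding an expected SAE is something the wording allows, not something the protocol instructs.

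The reply is also right about (b). Because causality may follow later, (b) need not be a causality verdict, and the next paragraph covers unrelated events expressly. Only (d) is a firm contradiction.

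A reader might infer more, and four such inferences are not supported.

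- **That the 7- and 15-day regulatory clocks would start late for expected events.** Those clocks apply to SUSARs, which are unexpected by definition. An event correctly classed as expected has no such clock.
- **That bradycardia shows the gap.** Section 9.3 says that sofosbuvir with another antiviral and amiodarone "may cause serious symptomatic bradycardia such as near-fainting or fainting, dizziness or light-headedness", but the same paragraph excludes subjects on amiodarone. Section 2.3 does mention bradycardia with sofosbuvir. Whether it counts as expected depends on the Investigator's Brochure, which is not at hand.
- **That liver events are known risks that would be filtered out.** Section 2.3 names fatigue, headache and nausea as the most frequent reactions. In stage 2, section 9.7 makes a single patient meeting the ALT/AST stopping criteria a reason to convene the DSMB, whatever its expectedness.
- **That expected SAEs would reach the sponsor only through the AE CRF.** Sections 15.2.1 and 15.2.2 both require the SAE form as well, so this describes conduct that the protocol forbids.

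**Conclusion.** The point holds as an internal inconsistency with a consequence for safety reporting. For an expected SAE, section 15.2.2 states two incompatible rules for the same report to the same recipient. The 24-hour rule for all SAEs is clearly the better supported of the two, so the practical risk is an occasional lapse at a site that follows the opening list literally, not systematic under-reporting.

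The documents give no SAE counts or expectedness classifications, so the number of reports at risk cannot be estimated. There is no effect on sample size, power or the analysis of SVR12.

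The conclusion assumes that the introductory sentence and (d) carry their ordinary meaning. A plausible explanation, which is an inference, is that criteria intended for expedited regulatory reporting were placed in the site-to-sponsor step. A correction is worth making because the conflict concerns serious events and is simple to remove.

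**What to change.** Make three changes to section 15.2.2.

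1. Delete the words *and unexpected* from (d).
2. State that the four items are the minimum content of an initial report and do not narrow the 24-hour rule for all SAEs. Word (b) as *study drug(s), if any received*. The words *if any* matter: requiring a drug to have been received would leave out pre-dose and screening-failure SAEs, which sections 6.3, 15 and 15.2.1 require to be captured.
3. State that the sponsor assesses expectedness after receipt, and only for the SUSAR timelines at the end of the section.

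The cost is a wording amendment and a reminder to sites. Nothing is added to what the table already requires, and no treatment rule, endpoint or analysis changes.

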15.3. Grading of Adverse Event severity

All toxicities and intensity of AEs will be evaluated by the investigator ad graded according to the DAIDS AE grading table version 2.0 / November 2014 (see Appendix II).

The decision to continue, put the study on hold or discontinue therapy is applicable to both drugs, sofosbuvir and ravidasvir, whatever the assumed relationship between one or both drugs and an adverse event. Using either drug alone may not only result in virological failure, but also may select resistance mutations which may jeopardize future therapy.

- Grade 1 and 2 Adverse Event
 - o Continue study treatment
- Grade 3 Adverse Event
 - For clinical events, or while awaiting a repeat assessment / confirmation as soon as possible (at most within 1 week) of an abnormal laboratory test the study treatment can be continued upon the judgment of the site investigator.
 - If repeat assessment of an abnormal laboratory test confirms Grade 3 toxicity and if the site investigator considers that the toxicity is possibly, probably, or definitely related to one or both study drugs, the treatment should be put on hold and laboratory values will be followed weekly and notified to the research team within 72 hours. Management of adverse events probably not related to study drugs will be determined on a case-by-case basis at the discretion of the site investigator.

- If toxicity resolves to ≤ Grade 2 within 7 days, study treatment can be restarted for the remaining planned treatment duration.
- If Grade 3 toxicity persists for >7 days, restart of the treatment will be under judgement of investigator in consultation with the sponsor.

If Grade 3 recurs to > Grade 3 after reintroduction of study drugs, treatment must be permanently discontinued. The site investigator and the study team will consult each other on treatment options on a case-by-case basis.

• Grade 4 Potentially-Life-Threatening Adverse Event

- If the site investigator and the study team consider that the adverse event is possibly, probably, or definitely related to one of the study drugs, the dual study treatment should be withheld and the study team be notified within 24 hours. For abnormal laboratory tests, repeat assessment/confirmation should be done as soon as possible (at most within 1 week).
- If repeat assessment confirms Grade 4 toxicity and site investigator and the study team consider that the adverse event may be related to the study drug, the study drug should be permanently discontinued.
- If repeat assessment shows Grade 3 toxicity, clinicians should continue to withhold the study drug and follow abnormal laboratory values weekly and notify the team within 72 hours.
- If toxicity resolves to < Grade 2 within 7 days, the study drug can be restarted from when it stopped for the remaining treatment duration. Restart of the treatment will be under the judgement of investigator in consultation with the sponsor.
- If >Grade 3 toxicity recurs after reintroduction of the study drug, the study drug must be permanently discontinued.
- Subjects who prematurely discontinue study treatment will continue to be followed at scheduled study visits as indicated in the schedule of evaluations.

In case of AEs that are not described in the DAIDS AE grading table version 2.0 / November 2014, the Investigator will use the terminology "mild", "moderate", "Severe" or "life-threatening" to describe the maximum severity of the adverse event.

- Mild: The subject is aware of the event or symptom, but the event or symptom is easily tolerated (e.g. no reduction in daily activities is required).
- Moderate: The subject experiences sufficient discomfort to interfere with or reduces his or her usual level of activity.
- Severe: Significant impairment of functioning: the subject is unable to carry out usual activities and/or the subject's life is at risk from the event.
- Life threatening: refers to an event/reaction in which the patient was at risk of death at the time of the event/reaction; it does not refer to an event/ reaction which hypothetically might have caused death if it were more severe.

When the intensity of an AE changes over time, each change in intensity will be recorded in the source documents until the event resolves. However, only one AE and the maximum intensity will be recorded in the CRF for each separate event. If the AE resolves but then recurs, each will be recorded as a separate AE, with the appropriate start and stop times.

Note: It is to be noted the distinction between severity and seriousness of adverse events. A severe adverse event is not necessarily a serious event.

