9.7. Discontinuation and interruption of treatment

Treatment may be discontinued:

- upon request of the subject, following counselling on the potential consequences and risks of antiviral discontinuation
- upon request of the primary care provider if s/he thinks that the it is no longer in the best interest of the subject,
- if, after discussion with the study team, the investigator judges that the subject is at significant risk of failing to comply with the provisions of the protocol thus compromising the validity of the study results,

- in case of HCV virological failure,
- in occurrence of serious adverse events deemed to be related to the study drugs or possibly interfering with therapy and upon consultation with the DSMB. Patient's follow-up will continue as follow-up visits in protocol and unscheduled visits are allowed as decided by investigators.
- upon recommendation of the Data and Safety Monitoring Board (DSMB) and,
- at the discretion of the IRB, relevant regulatory agency, any other government agency as part of their duties to protect the welfare of subjects

The study team must be informed, as soon as possible, when a subject comes off study treatment due to an AE. Restart of treatment after any interruption must be discussed and agreed on a case by case basis with the investigator and agreed with the sponsor.

Subjects who prematurely discontinue study treatment (i.e., prior to completion of their assigned dosing period) will complete all end of treatment evaluations, will remain on study and complete all post treatment visits, except if they have withdrawn consent.

If applicable, additional unscheduled post-treatment safety follow-up will be determined by the site investigator.

In stage 2, the following treatment stop criteria^[65] will apply for any patient from stage 2 study with:

- ALT/AST > 8x ULN
- ALT/AST remains > 5x ULN over 2 wks
- ALT/AST > 3x ULN & T Bili > 2x ULN or INR > 1.5
- ALT/AST > 3x ULN with symptoms (e.g. fatigue, nausea and vomiting, right upper quadrant of abdomen pain, fever, rash) or eosinophilia

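### For Stage 2 ALT/AST elevations graded 3 or 4, Protocol 15.3 permits continued dosing or restart where 9.7 requires a stop or sponsor agreement, and neither section refers to the other

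*Protocol*

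**What the plan says.** **Protocol 9.7 (Discontinuation and interruption of treatment).** The treatment stop criteria "will apply for any patient from stage 2 study with" any one of four findings:

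- ALT/AST above 8 times ULN;
- ALT/AST staying above 5 times ULN over two weeks;
- ALT/AST above 3 times ULN together with total bilirubin above 2 times ULN or INR above 1.5;
- ALT/AST above 3 times ULN with symptoms or eosinophilia.

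None depends on grade or on a causality judgement. Only the second needs serial values. The same section requires sponsor agreement for restart after any interruption, advises in general against rechallenge above 5 times ULN, and calls a DSMB meeting if a single patient meets a criterion.

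**Protocol 15.3 (Grading of Adverse Event severity).** This ladder applies to all toxicities.

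- *Grade 3, repeat pending (at most one week):* "the study treatment can be continued upon the judgment of the site investigator".
- *Grade 3, after the repeat:* if it "confirms Grade 3 toxicity and if the site investigator considers that the toxicity is possibly, probably, or definitely related" to a study drug, "the treatment should be put on hold and laboratory values will be followed weekly". Otherwise, "Management of adverse events probably not related to study drugs will be determined on a case-by-case basis", at the site investigator's discretion.
- *Grade 3, restart:* "If toxicity resolves to ≤ Grade 2 within 7 days, study treatment can be restarted for the remaining planned treatment duration". If the toxicity lasts longer than 7 days, the sponsor is consulted.
- *Grade 4:* by joint judgement of the site investigator and study team, if "the adverse event is possibly, probably, or definitely related to one of the study drugs, the dual study treatment should be withheld". On restart: "Restart of the treatment will be under the judgement of investigator in consultation with the sponsor".

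Section 15.3 does not mention 9.7, Stage 2 or ALT/AST. Section 9.7 does not mention 15.3 or the grades. Neither says which prevails.

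**The concern.** The same Stage 2 subject, with the same laboratory value, falls under two sets of dosing instructions. One says stop. The other makes the hold depend on grade, confirmation and attribution. An investigator who has just graded a toxicity will naturally turn to 15.3, and nothing there points to 9.7.

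What is at stake is hepatic safety, in a population that section 16.1.3 expects to include up to 50% with compensated cirrhosis, and consistency of conduct between sites. A subject whom 9.7 would stop could stay on drug, or could be restarted without the sponsor agreement that 9.7 demands.

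**Working it through.** No sample size, power or error rate is involved, and the protocol gives no figure of its own to reproduce. The check is a comparison of the two sections, limited to values graded 3 or 4, with one piece of arithmetic.

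**1. Causality.** Take a Stage 2 subject with ALT just above 8 times ULN, judged probably not related.

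- 9.7: stop.
- 15.3, if Grade 3: the hold condition is not met even after a confirming repeat, and management is at the site investigator's discretion.
- 15.3, if Grade 4: the condition for withholding is not met, and nothing else in the ladder requires a stop.

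The sections differ at both grades.

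**2. Timing.** This applies only at Grade 3, and only to the three criteria that need no serial values. The two-week persistence criterion requires repeated values anyway.

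- 9.7: stop when the criterion is met; no confirmatory repeat is stated.
- 15.3: dosing can continue while a repeat is awaited, for at most one week.

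Both drugs are taken once daily (section 9.1), so the ceiling is 7 further daily doses of the regimen:

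- 12-week course: 12 × 7 = 84 dosing days; 7/84 = 8.3%.
- 24-week course: 24 × 7 = 168 dosing days; 7/168 = 4.2%.

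**3. Restart.**

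- 9.7: restart after any interruption must be agreed with the sponsor.
- 15.3, Grade 3 resolving within 7 days: restart is allowed and the sponsor is not mentioned.
- 15.3, Grade 3 beyond 7 days, and the Grade 4 restart: the sponsor is mentioned.

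Because the neighbouring steps name the sponsor, a site could read the silence in the first as deliberate.

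**4. Precedence.** Neither section contains a cross-reference or an order of precedence. The amendment log in Appendix IV records a clarification on rechallenge in 9.7 but says nothing about how 9.7 relates to 15.3.

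**5. Reach.** Stage 2 plans 300 subjects. Only those who meet a 9.7 criterion on treatment are affected, and the protocol gives no rate from which to estimate their number.

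**The case against.** The strongest reply is that the rules are already ordered. Section 9.7 is mandatory and confined to one stage and one laboratory signal, while the 15.3 wording at issue is permissive or silent. A discretion to continue does not displace a specific duty to stop, and the sponsor-agreement rule for any interruption already covers a Grade 3 hold. A site that reads 9.7 as governing can satisfy both sections. This largely stands and keeps the point minor. It does not remove it: that reading has to be inferred, and a stated permission to keep dosing or restart still meets a stated stop or approval rule for the same patient.

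It might also be said that 15.3 disregards causality, because its opening says that dosing decisions apply to both drugs whatever the assumed relationship. That sentence means that the two drugs are continued or stopped together. It does not cancel the relatedness conditions that follow.

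Three stronger readings are tempting but unsupported.

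- *A reader might infer that a subject judged not related could stay on drug unchecked until the next four-weekly chemistry.* The Grade 3 repeat is itself due within a week, section 15.2.1 requires all adverse events to be monitored to outcome whatever their attribution, and the two-week criterion in 9.7 needs serial values. No such interval is claimed.
- *A reader might infer that the conflict extends to Grades 1 and 2, where 15.3 continues treatment.* The DAIDS cut-offs are not in the document, since Appendix II shows only a heading, so it cannot be shown which qualifying values would fall there.
- *A reader might infer that the simple cure is for 9.7 to override 15.3.* That would weaken protection. Section 15.3 requires permanent discontinuation for a confirmed, possibly related Grade 4 event and on recurrence at the stated grade after reintroduction, whereas the rechallenge wording in 9.7 is softer.

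**Conclusion.** The point holds as a minor patient-safety inconsistency. For Stage 2 ALT/AST elevations graded 3 or 4, 15.3 permits three things that 9.7 does not:

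- up to one more week of dosing while a Grade 3 repeat is awaited;
- no hold when the event is judged not related;
- restart after a Grade 3 event that resolves within 7 days, without naming sponsor agreement.

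Only the first can be quantified, at the ceiling of 7 daily doses shown above. That is an upper limit, not an expected delay, because the repeat is due as soon as possible and the investigator may stop at once.

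The conclusion assumes that the qualifying value is graded 3 or 4 and that the site acts on 15.3 without turning to 9.7. It does not support a claim that the sections cannot both be obeyed. Nor does it support a claim about SVR12, the sample size or the primary analysis. The DSMB trigger in 9.7 applies whatever dosing action is taken and remains a separate safeguard.

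**What to change.** Add a paragraph to 15.3, before the grade list, along these lines:

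> In Stage 2, a subject meeting any ALT/AST criterion in section 9.7 stops treatment when that criterion is met, regardless of grade or causality and without waiting for the confirmatory repeat below. Any restart must be agreed with the sponsor and meet the 9.7 rechallenge conditions. For these ALT/AST events, where 9.7 and 15.3 differ, the stricter rule applies, and the permanent-discontinuation rules in 15.3 remain in force.

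In the Grade 3 step for resolution within 7 days, add that restart must be agreed with the sponsor, as 9.7 requires.

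The cost is one paragraph, one clause and a memo to sites. No extra patients, visits or tests are needed.
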